## List of abbreviations

ACS	acute coronary syndrome
ADA	American Diabetes Association
AE	adverse event
ALT	alanine aminotransferase
ANOVA	Analysis of Variance
a.m.	ante meridiem (Latin for before noon)
AP	alkaline phosphatase
AST	aspartat aminotransferase
BHI 30	biphasic human insulin 30
BIAsp 30	biphasic insulin aspart 30
BID	twice daily
BMI	body mass index
CD	compact disc
CNS	central nervous system
CPMP	Committee for Proprietary Medicinal Products
CRF	case report form
CRO	contract research organisation
CTA	Clinical Trial Application
CTR	clinical trial report
CV	cardiovascular
CV(stat sect.)	coefficient of variance
CVD	cardiovascular disease
DFU	directions for use
DPP-4	Dipeptyl peptidase-4
DUN	dispensing unit number
EAC	event adjudication committee
ECG	electrocardiogram
eCRF	electronic case report form
EDC	electronic data capture
EMA	European Medicines Agency
FAS	Full Analysis Set
FDA	Food and Drug Administration (US)
FDAAA	Food and Drug Administration Amendments Act
FPG	fasting plasma glucose
FPFV	first patient first visit
FU	Follow up visit
GCP	Good Clinical Practice
GLP-1	glucagon like peptide 1
HbA 1c	glycosylated haemoglobin
HDL	high density lipoprotein
hh:mm	hour hour:minute minute
HI	human insulin

IAsp	insulin aspart
IB	investigator's brochure
ICH	International Conference on Harmonisation
ICMJE	The International Committee of Medical Journal Editors
ID	identification
IDeg	insulin degludec
IDegAsp 30	insulin degludec/insulin aspart (70 vol% insulin degludec + 30 vol% insulin aspart) 100 U/mL also known as IDegAsp 30
IDF	International Diabetes Federation
IEC	Independent Ethics Committee
IMP	Investigational Medicinal Product
IRB	Institutional Review Board
ITT	intention to treat
IUD	Intrauterine device
iv	intravenous
IWRS	interactive web response system
LDL	low density lipoprotein
LOCF	Last Observation Carried Forward
LPFV	last patient first visit
LPLV	last patient last visit
LSMeans	estimated mean treatment effects
MAO	monoamine oxidase
MedDRA	Medical Dictionary for Regulatory Activities
MI	myocardial infarction
NCR	non carbon required
NIMP	non-investigational medicinal product
NYHA	New York Heart Association
OAD	oral antidiabetic drug
OC	oracle clinical
OD	once daily
PDF	portable document format
PG	plasma glucose
PP	per protocol
PRO	patient reported outcome
SAE	serious adverse event
SAS	statistical analysis system
sc	subcutaneous
SD	standard deviation
SF-36	short form with 36 questions (health related quality of life questionnaire)
SFDA	State Food and Drug Administration
SGOT	serum glutamic oxaloacetic transaminase
SGPT	serum glutamic pyruvic transaminase
SMPG	self-measured plasma glucose
SPC	summary of product characteristics

Protocol  
Trial ID: NN5401-3598  
EudraCT No.: 2011-000085-36  
UTN: U1111-1118-8578

~~CONFIDENTIAL~~

Date:  
Version:  
Status:  
Page:

31 May 2017  
4.0  
Final  
9 of 102

**Novo Nordisk**

SU	sulphonylurea
SUSAR	suspected unexpected serious adverse reaction
TEAE	Treatment Emergent Adverse Event
TMM	Trial Materials Manual
TRIM-D	Treatment Related Impact Measure - Diabetes
T-T-T	treat-to-target
TZD	thiazolidinedione
U	Unit
US	United States

# 1 Summary

## Objectives and endpoints:

### Primary objective

To confirm the efficacy of IDegAsp 30 twice daily (BID) ± metformin in controlling glycaemia with respect to change from baseline in glycosylated haemoglobin (HbA1c) after 26 weeks of treatment. This is done by comparing the difference in change from baseline in HbA1c after 26 weeks of treatment between IDegAsp 30 and BIAsp 30 both BID ± metformin, to a non-inferiority limit of 0.4%, and if non-inferiority is confirmed, to a superiority limit of 0%.

### Secondary objectives

To confirm superiority of IDegAsp 30 BID ± metformin against BIAsp 30 BID ± metformin after 26 weeks of treatment in terms of:

- fasting plasma glucose (FPG) measured at central laboratory
- treatment emergent confirmed nocturnal hypoglycaemic episodes
- treatment emergent confirmed hypoglycaemic episodes
- body weight
- frequency of responders for HbA1c (<7.0 %) without confirmed hypoglycaemic episodes

To compare efficacy and safety of IDegAsp 30 BID ± metformin against BIAsp 30 BID ± metformin after 26 weeks of treatment in terms of:

- 9-point profile self-measured plasma glucose (SMPG)
- 2-point profile (SMPG) for dose adjustments
- frequency of responders for HbA1c targets
- adverse events (AEs)
- confirmed hypoglycaemic episodes
- clinical and laboratory assessments
- insulin dose
- insulin antibodies
- patient reported outcomes (PRO)

### Primary endpoint

Change from baseline in HbA1c (%) after 26 weeks of treatment (analysed by central laboratory).

### Key secondary endpoints

- Change from baseline in FPG after 26 weeks of treatment (analysed by central laboratory)

- Number of treatment emergent nocturnal confirmed hypoglycaemic episodes during 26 weeks of treatment
- Number of treatment emergent confirmed hypoglycaemic episodes during 26 weeks of treatment
- Change from baseline in body weight after 26 weeks of treatment
- Responder without hypoglycaemic episodes ( $HbA_{1c} < 7.0\%$  after 26 weeks of treatment and no confirmed hypoglycaemic episodes during the last 12 weeks of treatment or within 7 days after the last randomised treatment including only subjects exposed for at least 12 weeks)
- Incidence of treatment emergent adverse events (TEAEs) during 26 weeks of treatment

### **Trial design**

This is a 26 week, randomised, controlled, open label two-arm, parallel-group trial. The trial is conducted as a treat-to-target (T-T-T) trial.

Total trial duration for the individual subject will be approximately 31 weeks.

### **Trial population**

An expected number of 537 subjects with type 2 diabetes inadequately controlled on OD or BID premix/selfmix or basal insulin with or without metformin qualifying for intensification of therapy and who comply to the in- and exclusion criteria will be randomly allocated in a 2:1 manner into the two treatment groups.

### **Key inclusion criteria**

- Informed consent obtained before any trial-related activities. Trial-related activities are any procedures that are carried out as part of the trial, including activities to determine suitability for the trial
- Male or female  $\geq 18$  years of age
- Type 2 diabetes mellitus (diagnosed clinically) for  $\geq 6$  months
- Insulin treated subjects on current treatment: basal insulin, premixed insulin or a self-mixed insulin regimen, all administered once daily (OD) or BID with or without metformin. The treatment regimen should have remained unchanged for at least 8 weeks prior to randomisation
- $HbA_{1c}$  7.0-10.0 % (both inclusive) by central laboratory analysis
- Body mass index (BMI)  $\leq 40.0$  kg/m^2

### **Key exclusion criteria**

- Treatment with sulphonylureas, meglitinides, DPP-4 inhibitors, alpha-glycosidase inhibitors within 8 weeks prior to screening (Visit 1) or thiazolidinediones (TZDs) or GLP-1 receptor agonists within 12 weeks prior to screening (Visit 1)
- Anticipated change in concomitant medication known to interfere significantly with glucose metabolism, such as systemic corticosteroids, beta-blockers and monoamine oxidase (MAO) inhibitors
- Anticipated significant lifestyle changes during the trial according to the discretion of the investigator, e.g. shift work (including permanent night/evening shift workers), as well as highly variable eating habits
- Cardiovascular disease, within the last 6 months prior to screening (Visit 1), defined as: stroke; decompensated heart failure NYHA class III or IV; myocardial infarction; unstable angina pectoris; or coronary arterial bypass graft or angioplasty
- Any clinically significant disease or disorder, except for conditions associated with type 2 diabetes, which in the investigator's opinion could interfere with the results of the trial
- Previous participation in this trial. Participation is defined as screened.
- Known or suspected hypersensitivity to trial products or related products

### **Key assessments**

- HbA1c
- FPG
- SMPG profiles
- AEs
- Hypoglycaemic episodes
- Body weight
- Insulin antibodies
- PROs

### **Trial products**

- IDegAsp 30 100 U/ml, 3 ml pre-filled pen PDS290 (FlexTouch®)
- Biphasic insulin aspart 30 (BIAsp 30) (NovoMix® 30), 100 U/ml, 3 ml pre-filled pen (FlexPen®)
- Biphasic human insulin 30 (BHI 30, Novolin® 30), 100 U/ml prefilled pen (FlexPen®). For insulin coverage during the follow-up period.

All the insulin products are for subcutaneous (sc) injection

## 2 Flow chart

Trial procedures are outlined in [Table 2-1](#) and [2-2](#).

**Table 2–1 Flow chart**

Trial NN54-01-3598	Type 2	Screen	Rand	0-26 weeks														FU1	FU2
Visit Number (V)	V1	V2	V3	V4	V6	V8	V10	V12	V14	V16	V18	V22	V26	V28	V29				
 Phone Contact number (P)  (For details see separate flow chart)																P30			
Time of visit (weeks)	-1	0^2	1	2	4	6	8	10	12	14	16	20	24	26	27	30^5			
Visit window  (days)			±3	±3	±3	±3	±3	±3	±3	±3	±3	±3	±3	±3	-3	+5	+3		
SUBJECT RELATED INFO/ASSESSMENTS																			
Informed consent	x																		
In/Exclusion criteria	x	x																	
Randomisation		x																	
Withdrawal criteria			x	x	x	x	x	x	x	x	x	x	x	x	x				
Demography	x																		
Diagnosis of diabetes	x																		
Concomitant ill/ medical history	x																		
Concomitant medication	x	x	x	x	x	x	x	x	x	x	x	x	x	x	x	x			
Height	x																		
Body weight	x	x 							x 		x 				x 				
EFFICACY																			
Fasting plasma glucose 		x							x		x				x				
HbA 1c	x	x					x		x		x	x	x		x				
2-point profile 			x	x	x	x	x	x	x	x	x	x	x	x	x				
9-point profile 		x							x		x				x				
SAFETY																			
Adverse events	x	x	x	x	x	x	x	x	x	x	x	x	x	x	x	x	x 		
Insulin antibodies 		x							x						x	x			
Biochemistry	x														x				
Haematology	x														x				
Lipids 		x													x				
Urinalysis by stick	x														x				
Pregnancy test 	x														x				
Urine albumin/creatinine ratio (urinalysis)		x													x				
ECG – 12 lead 	x														x				
Eye examination  (fundoscopy/fundus photography)	x														x				
Hypoglycaemic episodes		x	x	x	x	x	x	x	x	x	x	x	x	x	x	x			
Physical examination	x														x				
Vital signs	x														x				
OTHER ASSESSMENTS																			
PRO questionnaires 		x 							x 						x 				
End of trial 																	x		
TRIAL MATERIAL																			
IWRS session	x	x			x		x		x		x	x		x	x				
Drug accountability (IWRS)					x		x		x		x	x		x	x				

Trial NN54-01-3598	Type 2	Screen	Rand	0-26 weeks														FU1	FU2
Visit Number (V)	V1	V2	V3	V4	V6	V8	V10	V12	V14	V16	V18	V22	V26	V28	V29				
 Phone Contact number (P)  (For details see separate flow chart)			P5	P7	P9	P11	P13	P15	P17	P19	P23	P27			P30				
Time of visit	(weeks)	-1	0^2	1	2	4	6	8	10	12	14	16	20	24	26	27	30^5		
Visit window 	(days)			±3	±3	±3	±3	±3	±3	±3	±3	±3	±3	±3	-3	+5	+3		
Dispensing visit		x			x		x		x		x	x		x					
Dispense direction for use/package leaflet		x			x		x		x		x	x		x					
First date, doses and time points on trial insulin				x															
Dates and doses of trial insulin on three days prior to visit				x	x	x	x	x	x	x	x	x	x	x	x				
New dose of trial insulin				x	x	x	x	x	x	x	x	x	x	x					
Last date, dose and time point on trial insulin															x				
BHI 30, date and dose 																x			
REMINDERS																			
Attend visit fasting 		x								x		x			x	x			
Notes made if change in metformin dose or treatment				x	x	x	x	x	x	x	x	x	x	x	x				
Make appointment for eye examination													x						
Handling/training of product/device 		x	x												x				
Instruction/handout of glucose meter 		x																	
Hand-out/instruction/collect diary		x	x	x	x	x	x	x	x	x	x	x	x	x	x	x			
Sign off casebook																	x		

1. A phone contact may be converted to a visit if for instance further titration attention is needed.
2. Randomisation will take place no later than 14 days after the screening visit (Visit 1). Randomisation can only take place if the results of the screening visit assessments (including blood sampling) are available and reviewed.
3. Time of visit is always calculated related to actual visit date of the randomisation visit.
4. Fasting visits: The subjects must attend Visits 2, 14, 18, 28 and 29 fasting, having consumed only water since midnight for measurement of lipids (Visits 2 and 28), weight and fasting plasma glucose (Visits 2, 14, 18, 28) and insulin antibodies (Visits 2, 14, 28, 29). No diabetes medication is allowed before these visits. If the subjects attend the site in a non-fasting condition the visit should be re-scheduled within the next two working days.
5. Two follow-up (FU) Visits are planned. FU1 (V29) must take place 7-12 days after the actual date Visit 28 is performed. FU 2 (P30) should take place 30 days after Visit 28.
6. 2-point profiles (SMPG): pre-breakfast and pre-dinner (main evening meal) SMPGs should be taken throughout the trial for titration/dose adjustments. Please see appendix A for details.
7. 9-point profiles (SMPG) must be started in the morning 2 days before Visits 2, 14, 18 and 28. Measurements are to be performed before and after (90 min after the start of the meal) breakfast, lunch, main evening meal, before bedtime, at 4 am and before breakfast on the following day. Please note that the 9-point profile (SMPG) is overlapping with the 2-point profile (SMPG).
8. Pregnancy test: At Visits 1 and 28 a blood pregnancy test will be performed in women of child bearing potential. During the trial a urine pregnancy test will be performed if a menstrual period is missed or pregnancy is suspected. If at phone contacts, subjects report missed menstrual period, the subject will have to attend the site for a urine pregnancy test.
9. The baseline ECG should be performed between the screening Visit 1 and the randomisation Visit 2, and results must be available before randomisation. The end of treatment ECG should be performed at Visit 28.
10. A funduscopy or fundus photography performed for any reason unrelated to this trial within 12 weeks prior to screening visit (Visit 1) is acceptable provided no clinical symptoms suggestive of eye disease have occurred in the meantime. It is allowed to perform the Visit 1 funduscopy or fundus photography between Visit 1 and Visit 2. The results must be available prior to randomisation. Funduscopy/fundus photography performed within a period of three weeks before Visit 28 is acceptable if results are available at the visit and provided no clinical symptoms suggestive of eye disease have occurred in the meantime.

11. PRO questionnaires; A battery of PRO questionnaires will evaluate health related quality of life, treatment satisfaction and preferences. The PRO questionnaires should be filled in by the subject at the visits preferably after conclusion of all fasting related activities, but before any other trial related procedures.
12. At baseline (Visit 2) only SF-36 & TRIM-D will be completed by subjects. At visit 14 & visit 28 all PROs (SF-36, TRIM-D, TRIM-D Device, and Device Specific Questionnaires (DSQ) I & II will be filled in.
13. .BHI 30 date, dose and time point (breakfast/ main evening meal) on first day (V28), 2 days and 4 days, after Visit 28 and on the the last day before FU1 (Visit 29). No BHI 30 is taken in the morning of Visit 29.
14. Instruction to be done in the start of the study and if required, and at visit 28.
15. If prematurely withdrawal, the procedures for the last treatment visit (Visit 28) and the follow-up visits (FU1 (Visit 29) & FU2 (P 30)) must be performed if possible
16. Only cardiovascular events and AEs will be collected.

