#### **4.2.3.3 PRO**

The following questionnaires will be used to compare PROs and costs associated with hypoglycaemia between treatments:

- Health Related Quality of Life Questionnaire (SF-36)
- Treatment Satisfaction Questionnaire (treatment related impact measure-diabetes (TRIM-D) and treatment related impact measure-diabetes device (TRIM-D Device)
- Device Specific Questionnaires I and II

[figure not shown]

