Only endpoints derived after 26 weeks of treatment will be analysed statistically. Missing values will be imputed using the Last Observation Carried Forward (LOCF) method. LOCF has been a standard approach in diabetes trials for many years, and was used as the primary analysis in all degludec phase 3a trials. LOCF is considered to be an appropriate method in the context of treat-to-target trials, where subjects after withdrawal typically continue their therapy using commercially available insulin. In previous treat-to-target trials with degludec LOCF has generally provided similar results to alternative methods to handle missing data, such as repeated measures models and completer analyses. In this trial, similar sensitivity analyses will be made to examine the robustness of the LOCF method. All endpoints will be summarised descriptively at each visit by treatment and in total using observed data. After 26 weeks of treatment, descriptive statistics will be presented based both on observed and LOCF imputed data. Endpoints that are analysed untransformed and

endpoints that are not formally analysed are summarised by the arithmetic mean, standard deviation (SD), median, and minimum and maximum value. Endpoints that are analysed log-transformed are summarised by the geometric mean, CV, median, minimum and maximum value.

LOCF imputed data will be used as the basis for plotting data if not otherwise specified.

Presentation of results from a statistical analysis will include the estimated mean treatment effects (least-squares means [LSMeans]) for absolute values and change from baseline if applicable. Estimated mean treatment differences (or ratios) will be presented together with two-sided 95% confidence intervals for all endpoints analysed statistically. p-values will only be presented for the primary and the confirmatory secondary endpoints for which formal statistical testing will be performed. The other endpoints are considered supportive and explorative in nature and no p-values will be presented.

For endpoints measured over time mean values will be plotted to explore the trajectory over time. For survival endpoints, Kaplan-Meier plots are presented for each treatment. Data collected before randomisation will only be summarised descriptively.

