### 17.1 Sample size calculation

The primary objective of this trial is to confirm efficacy of IDegAsp 30 BID ± metformin in terms of glycaemic control.

This is done by showing that:

IDegAsp 30 BID ± metformin is non-inferior to BIAsp 30 BID ± metformin in terms of glucose lowering effect as assessed by change from baseline in HbA1c after 26 weeks of treatment using a non-inferiority margin of 0.4% (absolute). Sample size is determined based on this primary objective.

Throughout this section of the protocol the term “investigational product” will be used as a synonym for IDegAsp 30 and the term “comparator” will be used as a synonym for BIAsp 30 BID.

The non-inferiority margin of 0.4% (absolute) was chosen in accordance with the FDA guidance. Let D be the mean treatment difference for change in HbA1c (investigational product minus comparator). The null-hypothesis will be tested against the alternative hypothesis of non-inferiority as given by

$H_0: D > 0.4\%$  against  $H_A: D \leq 0.4\%$

Operationally the null-hypothesis will be rejected and non-inferiority considered confirmed if the upper bound of the two-sided 95% confidence interval for the mean HbA1c treatment difference is below or equal to 0.4%. This is equivalent to using a one-sided test of size 2.5%.

Sample size is determined using a t-statistic under the assumption of a one-sided test of size 2.5% and a zero mean treatment difference (i.e. D=0%). Based on experience from previous phase 3 trials in subjects with type 2 diabetes treated with insulin an estimate for the standard deviation (SD) of 1.3% for HbA1c will be used in the sample size calculation ([Table 17-1](#)). The sample size calculation is done using SAS 9.3.

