#### **17.9 Health economics and/or patient reported outcomes**

The following questionnaires will be used to compare PROs and costs associated with hypoglycaemia between treatments:

- SF-36
- TRIM-D and TRIM-D Device
- Device Specific Questionnaires I and II

For the questionnaires , SF-36 and TRIM-D the change in score (total score if appropriate) from baseline will be analysed separately using an ANOVA method with treatment, anti-diabetic therapy at screening and sex as fixed factors, and age and the relevant baseline value as covariates.

Protocol  
Trial ID: NN5401-3598  
EudraCT No.: 2011-000085-36  
UTN: U1111-1118-8578

~~CONFIDENTIAL~~

Date:	31 May 2017	Novo Nordisk
Version:	4.0	
Status:	Final	
Page:	88 of 102	

For the device questionnaire TRIM-D Device , which is not assessed at baseline, the score (total score if appropriate) will be analysed using an ANOVA method with treatment, anti-diabetic therapy at screening and sex as fixed factors, and age as covariate.

For Device Specific Questionnaires I and II, since there are no validated scoring algorithms, formal statistical analysis will not be conducted and only descriptive statistics will be presented.

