2.6 Health economics and/or patient reported outcomes

The following questionnaires will be used to compare PROs and costs associated with hypoglycaemia between treatments:

- SF-36^{4,5}
- TRIM-D⁶ and TRIM-D Device⁶
- Device Specific Questionnaires I and II⁷

For the questionnaires , SF-36 and TRIM-D the change in score (total score if appropriate) from baseline will be analysed separately using an ANOVA method with treatment, anti-diabetic therapy at screening and sex as fixed factors, and age and the relevant baseline value as covariates.

For the device questionnaire TRIM-D Device , which is not assessed at baseline, the score (total score if appropriate) will be analysed using an ANOVA method with treatment, anti-diabetic therapy at screening and sex as fixed factors, and age as covariate.

For Device Specific Questionnaires I and II, since there are no validated scoring algorithms, formal statistical analysis will not be conducted and only descriptive statistics will be presented.

3 Changes to the statistical analyses planned in the protocol

There were 2 minor changes to the statistical analyses planned in the protocol as described below:

- The mean PG at baseline as covariate in the analysis for the 2-point SMPG profiles was not included since the 2-point SMPG was not collected until visit 3.
- Last Observed Value (LOV) was defined to summarise efficacy data and replace LOCF in summary table.

4 References

1. EMEA-Committee for Proprietary Medicinal Products. CPMP/EWP/482/99 - Points to consider on switching between superiority and non-inferiority. 27-2-2000.
2. Food and Drug Administration. Food and Drug Administration, Code of Federal Regulations, Guidance for Industry, Diabetes Mellitus: Developing Drugs and Therapeutic Biologics for Treatment and Prevention. Draft Guidance. 2008.
3. Rubin DB. Inference and missing data. *Biometrika* 1976; 63(3):581-592.
4. Ware JE, Jr., Sherbourne CD. The MOS 36-item short-form health survey (SF-36). I. Conceptual framework and item selection. *Med Care* 1992; 30(6):473-483.

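### The TRIM-D Device analysis uses no baseline questionnaire score, although the companion TRIM-D score is collected at Visit 2 and could be added as a covariate at almost no cost

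*Protocol*

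**What the plan says.** Footnote 12 to Table 2–1 of the Protocol sets the questionnaire schedule. For Visit 2 it says: "At baseline (Visit 2) only SF-36 & TRIM-D will be completed by subjects". For the later visits it says: "At visit 14 & visit 28 all PROs (SF-36, TRIM-D, TRIM-D Device, and Device Specific Questionnaires (DSQ) I & II will be filled in". TRIM-D Device therefore has no pre-treatment value.

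Protocol 4.2.3.3 puts TRIM-D and TRIM-D Device in a single bullet, with the same literature reference. The bullet opens: "Treatment Satisfaction Questionnaire (treatment related impact measure-diabetes (TRIM-D".

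Protocol 17.9 gives the consequence for the analysis: "For the device questionnaire TRIM-D Device , which is not assessed at baseline, the score (total score if appropriate) will be analysed" by ANOVA. The terms are treatment, the four-level screening-therapy factor, sex and age. SAP 2.6 repeats this model unchanged. For SF-36 and TRIM-D, the same SAP section analyses change from baseline and includes "age and the relevant baseline value as covariates".

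Protocol 17 limits p-values to the primary and confirmatory secondary endpoints and adds: "The other endpoints are considered supportive and explorative in nature and no p-values will be presented". TRIM-D Device falls in this last group, so its estimate and 95% confidence interval are all that will be reported inferentially.

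**The concern.** The plan usually adjusts a continuous endpoint for its own starting level: HbA1c, FPG, body weight, lipids, the 9-point profile summaries, SF-36 and TRIM-D are all handled this way. TRIM-D Device is an exception because its own baseline does not exist. That explains why its own baseline is absent. It does not explain leaving out the companion score.

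Every subject enters on insulin (inclusion criterion 4), so a treatment-satisfaction score at Visit 2 is meaningful for all of them. The first trial dose comes after the randomisation visit is completed, so the score precedes trial treatment and is a legitimate covariate. If it predicts the later device rating, the planned interval is wider than it needs to be, and a chance difference between arms in baseline satisfaction passes into the estimate unadjusted. What is at stake is the precision of one supportive comparison.

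**Working it through.** **Inputs from the documents.** Randomised numbers are 358 and 179, total 537 (Protocol Table 17–3). Expected completers are 450 (Protocol 6.1). The planned model terms are in Protocol 17.9 and SAP 2.6.

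**Input not in the documents.** r is the partial correlation between Visit 2 TRIM-D and week-26 TRIM-D Device, given treatment, screening therapy, sex and age. It is assumed, over the range 0.1 to 0.5.

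**The plan's own figure.** The documents state no SD, effect size or power for TRIM-D Device. The only sample size is for HbA1c, and it reproduces: with margin 0.4, SD 1.3, a "one-sided test of size 2.5% and a zero mean treatment difference (i.e. D=0" and 2:1 allocation, the noncentral t gives power 0.871 at 456 subjects, and 456 / 0.85 = 536.5, rounded up to 537. It says nothing about this endpoint.

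**Precision as planned**, in units of the model's residual SD, with full data and a normal approximation:

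- SE = sqrt(1/358 + 1/179) = 0.0915
- 95% half-width = 1.96 × 0.0915 = 0.179

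**Precision with the covariate.** Residual variance is multiplied by 1 − r², interval width by sqrt(1 − r²), and the equivalent sample size is 537 / (1 − r²).

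| r | Variance reduction | Half-width | Interval narrower by | Equivalent total N |
|---|---|---|---|---|
| 0.1 | 1% | 0.179 | 0.5% | 542 |
| 0.2 | 4% | 0.176 | 2.0% | 559 |
| 0.3 | 9% | 0.171 | 4.6% | 590 |
| 0.4 | 16% | 0.164 | 8.3% | 639 |
| 0.5 | 25% | 0.155 | 13.4% | 716 |

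With the 450 expected completers (300 and 150), SE = sqrt(1/300 + 1/150) = 0.100 and the planned half-width is 0.196. The percentage gains are the same.

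**Chance imbalance.** The between-arm difference in mean baseline TRIM-D has a 95% range of about ±0.18 of its own SD under randomisation. At r = 0.4, an imbalance at the edge of that range moves the unadjusted estimate by about 0.4 × 0.18 = 0.07 SD. Adjustment takes this out.

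**Cost.** The planned model estimates 7 parameters: intercept, treatment, three for screening therapy, sex and age. Residual degrees of freedom go from 537 − 7 = 530 to 529. The cost is about 1/529 = 0.19% of the variance, so the covariate pays for itself once r² exceeds about 0.0019, that is r above about 0.04.

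**The case against.** The strongest case against is that this is a preference. The two documents agree, state openly that there is no baseline, and follow a consistent rule: use an endpoint's own baseline if it exists, otherwise leave it out. SAP section 3 does the same for the 2-point SMPG means. Borrowing another instrument as a proxy is optional. This stands, and it is why the point is an improvement and not a correction.

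Next, the gain is unproven. A shared bullet and reference say nothing about correlation, and the documents give no items or scoring. Visit 2 TRIM-D reflects the previous treatment, whereas TRIM-D Device rates a pen first handed out at Visit 2, so a weak correlation is plausible. At r of 0.2 or less the gain is negligible. This stands too. What remains is the asymmetry: the possible loss is about 0.2% of the variance, while a moderate correlation gains several per cent of interval width.

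Third, the planned model can use a subject with no Visit 2 TRIM-D, whereas the adjusted model would drop that subject unless a rule is given. LOCF cannot supply a baseline where nothing precedes it. This is correct, and the fix includes a rule.

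Some stronger readings are tempting, and the documents do not support them:

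- A reader might infer that the analysis has no baseline adjustment at all. Screening therapy, sex and age are baseline variables and are in the model.
- A reader might infer bias. Under randomisation the planned comparison is unbiased, and its interval already allows for chance imbalance.
- A reader might infer that adjustment deals with subjective ratings in an open-label trial with two different pens. It corrects neither: reporting bias is untouched, and the pen difference is part of what is being compared.
- A reader might infer that TRIM-D Device should have been asked at Visit 2. The trial pen had not been used by then, so its absence is understandable.

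**Conclusion.** The point holds as a cheap improvement. A pre-treatment treatment-satisfaction score is already collected and is left out of the one formally analysed questionnaire model that has no baseline score of its own. Using it would probably narrow the TRIM-D Device interval by somewhere between 0.5% (r = 0.1) and 13% (r = 0.5), and would remove the linear effect of chance imbalance in baseline satisfaction.

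The size rests on an assumed r, a linear relation and near-complete data. It also assumes that the Visit 2 questionnaire is answered before the subject knows the allocation. The Protocol asks for questionnaires ahead of other visit procedures only as a preference; the existing baseline adjustments of SF-36 and TRIM-D depend on the same order. No confirmatory conclusion is affected.

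**What to change.** In Protocol 17.9 and SAP 2.6, add the Visit 2 TRIM-D total score as a covariate in the TRIM-D Device model, next to treatment, screening therapy, sex and age. State that a missing Visit 2 score is replaced by the overall baseline mean, taken over both arms, so that no subject is dropped. Both documents leave open whether total scores are formed, so the SAP should confirm that a TRIM-D total will be available or name the score to be used.

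The cost is one degree of freedom and one missing-covariate rule. No new data, visit or questionnaire is needed. If the sponsor prefers to keep the present model as the main one, the adjusted version can be pre-specified as a sensitivity analysis. Either change can be recorded in SAP section 3, which already lists a covariate change for the 2-point SMPG means.
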